3.4 Analysis Rules

3.4.1 Visit Windowing:

Primary endpoints analysis is performed at Visit 25 (week 56) and secondary endpoints are performed at Visit 19 (week 30), Visit 25 (week 56) and Visit 30 (week 82).

For subjects who prematurely discontinues trial product or subject and/or the subject’s LAR(s) withdraw consent, the investigator must aim to undertake procedures like those for the end of treatment (V25) as soon as possible, and a follow-up visit (V26) two weeks later.

The subjects were asked to attend additional visits depending on when the trial product discontinuation takes place during the trial:

- If the trial product is discontinued before V19 subjects were asked to attend three additional visits (V19x, V25x and V30x) taking place weeks 30, 56 and 82 after randomisation, respectively.
- If the trial product is discontinued after V19 and before V25 subjects were asked to attend two additional visits (V25x and V30x) taking place weeks 56 and 82 after randomisation, respectively.

The end of treatment (V25), and a follow-up visit (V26) collected for prematurely discontinued subject and withdrawn subjects did not exactly taken place in respective endpoint weeks (i.e., at week 30, week 56 and week 82). Hence these records will be reallocated to the respective weeks based on analysis day on when the assessments are done by visit windowing concept.

3.4.1.1 Visits windows:

Generally, visit-windows will be used for the data that is summarized by visit; they are based on the study evaluation schedule and comprise a set of days around the nominal visit day. For any assessment, there are the protocol defined scheduled visits around which visit windows were created to cover the complete range of days within the study.

In 4180 the visit windowing will be done only for V25 and V26 visits for prematurely discontinued/withdrawn subjects.

The visit windows are shown in [Table 3-1](#).

In this table, the days are counted since the date of randomization for both safety and efficacy assessments. These visit windows apply to measurements taken at every visit. For assessments collected less often different visit windows will be applied as detailed below.

When visit windows are used, all visits will be re-aligned, i.e., they will be mapped into one of the visit windows. For example, if the Week 4 visit of a subject is delayed and occurs on Day 46 instead of on Day 29, it will be re-aligned to visit window Week 8. In the case of major deviations from the visit schedule, or due to unscheduled visits, several assessments of a subject may fall in a particular visit window (either scheduled or unscheduled). Statistical approaches to handle multiple assessments in a given visit window are specified below.

In general, if two consecutive visits V_t and V_s are x days apart, the upper limit of the visit window for V_t will be $V_t+x/2$ and the lower limit for the visit V_s will be $V_s-x/2$ (if x is even, the lower limit for V_s will be $V_s-x/2+1$, and the upper limit for V_t will be $V_t+x/2$). The algorithm needs to ensure that visit windows are not overlapping and that there are no gaps, such that each assessment can be uniquely allocated to one visit window, e.g., if Week 8 visit is scheduled for day 57, Week 12 is scheduled at Day 85 and Week 16 is scheduled at Day 113, then the visit window for week 12 extends from Day 72 to Day 99.

Note: The lower limit of first visit will be assigned with -999 which accommodate all assessments occurred before the scheduled day.

The upper limit of last visit will be assigned with 999 which accommodate all assessments occurred after the scheduled day.

Table 3-1: Assessment windows for scheduled visits

Analysis Visit	Week	Scheduled Day	Visit Window
Visit 2 (screening)	week -14	-98	Day -999 to -91
Visit 3 (week -12)	week -12	-84	Day -90 to -70
Visit 5 (week -8)	week -8	-56	Day -69 to -42
Visit 7 (week -4)	week -4	-28	Day -41 to -21
Visit 8 (week -2)	week -2	-14	Day -20 to -7
Visit 9 (week 0)	Randomisation	1	Day -6 to 4
Visit 10 (week 1)	week 1	8	Day 5 to 11
Visit 11 (week 2)	week 2	15	Day 12 to 18
Visit 12 (week 3)	week 3	22	Day 19 to 25
Visit 13 (week 4)	week 4	29	Day 26 to 43
Visit 14 (week 8)	week 8	57	Day 44 to 71
Visit 15 (week 12)	week 12	85	Day 72 to 99
Visit 16 (week 16)	week 16	113	Day 100 to 127
Visit 17 (week 20)	week 20	141	Day 128 to 158
Visit 18 (week 25)	week 25	176	Day 159 to 193
Visit 19 (week 30)	week 30	211	Day 194 to 225
Visit 19x (week 30 follow-up)	week 30	211	Day 194 to 225
Visit 20 (week 34)	week 34	239	Day 226 to 253
Visit 21 (week 38)	week 38	267	Day 254 to 281
Visit 22 (week 42)	week 42	295	Day 282 to 309
Visit 23 (week 46)	week 46	323	Day 310 to 340

Analysis Visit	Week	Scheduled Day	Visit Window
Visit 24 (week 51)	week 51	358	Day 341 to 375
Visit 25 (week 56)	week 56	393	Day 376 to 400
Visit 25x (week 56 follow-up)	week 56	393	Day 376 to 400
Visit 26 (week 58)	week 58	407	Day 401 to 428
Visit 27 (week 64)	week 64	449	Day 429 to 470
Visit 28 (week 70)	week 70	491	Day 471 to 512
Visit 29 (week 76)	week 76	533	Day 513 to 554
Visit 30 (week 82)	week 82	575	Day 555 to 999
Visit 30x (week 82 follow-up)	week 82	575	Day 555 to 999

3.4.1.2 For parameters which are not collected at every visit (e.g. HEIGHT):

Visit windows defined in [Table 3-1](#) will be combined. For example, [Table 3-2](#) show visit windows for HEIGHT.

Table 3-2: Assessment windows for scheduled visits

Analysis Visit	Week	Scheduled Day	Visit Window
Visit 2 (screening)	week -14	-98	Day -999 to -56
Visit 8 (week -2)	week -2	-14	Day -55 to -7
Visit 9 (week 0)	week 0	1	Day -6 to 43
Visit 15 (week 12)	week 12	85	Day 44 to 148
Visit 19 (week 30)	week 30	211	Day 149 to 253
Visit 19x (week 30 follow-up)	week 30	211	Day 149 to 253
Visit 22 (week 42)	week 42	295	Day 254 to 344

Analysis Visit	Week	Scheduled Day	Visit Window
Visit 25 (week 56)	week 56	393	Day 345 to 484
Visit 25x (week 56 follow-up)	week 56	393	Day 345 to 484
Visit 30 (week 82)	week 82	575	Day 485 to 999
Visit 30x (week 82 follow-up)	week 82	575	Day 485 to 999

3.4.1.3 For parameters which are collected at ‘x’ visits:

For premature discontinued subjects a parameter such as ‘BODY_WEIGHT’, ‘HEIGHT’ is collected at additional visits like 19x, 25x and 30x, hence if the visit reallocation for these parameters and related parameters such as ‘BMI’, ‘BMI_SDS’ and ‘HEIGHT_SDS’ are reallocated to x visit instead of normal visit (i.e., visits 19, 25 and 30). Other parameters are reallocated to normal visits.

Note: Withdrawal subjects are reallocated to normal visits.

3.4.2 Analysis eligible records:

If the records are reallocated to the visit which is already collected, then the collected visit record is used for analysis instead of record which is reallocated to that visit.

if the subjects have records for both normal visit (Visit 19 (week 30)) and x visit (Visit 19x (week 30)) then the records which are reallocated are not eligible for analysis.

4 References

1. International Conference on Harmonisation. ICH Harmonised Tripartite Guideline. Guideline for Good Clinical Practice E6 (R1), Step 4. 10 June 1996.

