8.1.9 Withdrawal from trial

If a subject and/or the subject's LAR(s) withdraw consent, the investigator must aim to undertake procedures similar to those for the end of treatment (V25) as soon as possible, and a follow-up visit (V26) two weeks later.

If a subject and/or the subjects LAR(s) withdraw consent after end of treatment (V25), the investigator must aim to undertake procedures similar to those for the end of trial (V30) as soon as possible.

The end of trial form must be completed and final drug accountability must be performed even if the subject is not able to come to the trial site. A treatment discontinuation session must be made in IWRS. The case book must be signed.

Although a subject is not obliged to give his/her reason(s) for withdrawing consent, the investigator must make a reasonable effort to ascertain the reason(s), while fully respecting the subject's rights. Where the reasons are obtained, the primary reason for withdrawing consent must be specified on the end-of-trial form in the eCRF.

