1.1 Trial information

Trial design

This is a 56-week double-blind, randomised, parallel-group, placebo-controlled, multi-national trial followed by a 26-week period off study-drug. The trial will be conducted in pubertal adolescents with obesity aged 12 to less than 18 years. Subjects will be randomised 1:1 to receive liraglutide or placebo. The randomisation will be stratified according to pubertal and glycaemic status (see protocol Sections 5.2 and 11).

At least 30% of subjects will be from areas with lifestyle and nutrition comparable to those in the European Union. All subjects will undergo counselling in healthy nutrition and physical activity for weight loss and must be prescribed a structured programme from the beginning of the 12-week run-in period and continuing through the 26-week follow-up period off trial drug.

Primary objective

- To compare the efficacy of liraglutide versus placebo on weight loss in adolescent subjects with obesity after 56 weeks of treatment

Secondary objectives

- To compare the efficacy of liraglutide versus placebo on glycaemic control, cardiovascular risk factors and Impact of Weight on Quality of Life-Kids (IWQOL-Kids) in adolescent subjects with obesity after 30 and 56 weeks of treatment
- To compare the safety of liraglutide versus placebo in adolescent subjects with obesity after 30 and 56 weeks of treatment
- To examine the potential rebound effect from end of treatment at week 56 to week 82

Further details are described in the protocol section 4.2.

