3.2 Supportive secondary efficacy endpoints

- All the secondary supportive analysis will be performed on in-trial period.
- To analyse the change in BMI SDS from week 56 to week 82 subjects who have completed the treatment (treatment completers), only their assessment at week 56 will be considered as baseline. No change from week 56 to 82 will be calculated for treatment discontinued subjects and for withdrawn subjects unless they have week 56 visit assessment collected.
- Multiple imputation will not to be considered for change in BMI SDS from week 56 to 82 parameter if there is no missing assessment.
- Tanner stage and glycaemic category collected at randomisation visit will be considered as fixed effect while performing ANCOVA for change from baseline to week 30, 56 and 82 and change from week 56 to 82.
- For “percentage of subjects achieving $\geq 5\%$ reduction” and “Percentage of subjects achieving $\geq 10\%$ reduction” in baseline BMI at week 30, 56 and 82. Missing imputation will be handled as mentioned in section [2.3](#) with the baseline BMI as covariate instead of baseline BMI SDS.
- Body weight with standard units (Kg) will only be used in all summary and analysis outputs.

Below additional supportive secondary endpoint is been included in section [2.4](#)

- Change from baseline to 30 and 56 weeks in:
 - BMI SDS (%)

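### A V30 done early after withdrawal in follow-up has no clear windowing rule: one SAP sentence leaves it labelled week 82, while other SAP text and the SAP's own windows would move it

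*SAP*

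**What the plan says.** **How the record arises.** For consent withdrawn after V25, Protocol 8.1.9 states that "the investigator must aim to undertake procedures similar to those for the end of trial (V30) as soon as possible".

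**What the SAP windows.** SAP 3.4.1 repeats the protocol's V25/V26 procedure for early leavers and notes that these visits do not fall in the endpoint weeks. It concludes: "Hence these records will be reallocated to the respective weeks based on analysis day on when the assessments are done by visit windowing concept". It does not repeat the V30 procedure for withdrawal after V25. SAP 3.4.1.1 then limits the scope: "In 4180 the visit windowing will be done only for V25 and V26 visits for prematurely discontinued/withdrawn subjects".

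**What conflicts with that limit.** Further down in 3.4.1.1: "When visit windows are used, all visits will be re-aligned, i.e., they will be mapped into one of the visit windows". The illustration given is a delayed Week 4 visit, which is neither V25 nor V26. Table 3-1 and Table 3-2 both give V30 a window of its own.

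**What the record feeds.** SAP 3.4.1 takes Visit 30 as the week-82 analysis visit. SAP 3.2 calculates no week 56–82 change in BMI SDS for discontinued subjects or "for withdrawn subjects unless they have week 56 visit assessment collected". A subject who leaves during follow-up will normally have that assessment, so the early V30 can enter. The objective served is "To examine the potential rebound effect from end of treatment at week 56 to week 82".

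**The concern.** The SAP recognises that the visits of early leavers miss their nominal weeks. It corrects this for two of the three visits that Protocol 8.1.9 can displace and does not mention the third. A programmer who follows the sentence specific to this trial leaves an early V30 at week 82. A programmer who follows the general sentence and the tables moves it.

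The endpoints at stake are the change in BMI SDS to week 82, the week 56–82 changes (BMI SDS modelled, the others descriptive) and the 5% and 10% BMI responders at week 82. On the literal reading, a value taken a few weeks after stopping drug counts as 26 weeks off drug. Early placebo V30 values would also join the week-82 reference data from which SAP 2.3.2 imputes missing values.

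**Working it through.** **1. Reproduce the SAP's week-82 limits.** The rule in SAP 3.4.1.1 for two visits an even number of days x apart sets the later window's lower limit at its scheduled day − x/2 + 1.

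- Table 3-1: V29 is Day 533 and V30 is Day 575, so x = 42 and the limit is 575 − 21 + 1 = **555**, as printed.
- Table 3-2 (height): V25 is Day 393 and V30 is Day 575, so x = 182 and the limit is 575 − 91 + 1 = **485**, as printed.

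**2. Place an early V30.** Take withdrawal at week 60, which is Day 1 + 60 × 7 = 421. Time off drug is (421 − 393)/7 = 4 weeks, or 4/26 = 15% of the follow-up period.

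| Reading | Analysis week for Day 421 |
|---|---|
| Windowing for V25 and V26 only | Week 82 |
| Table 3-1 (V26 window, Days 401–428) | Week 58 |
| Table 3-2 (week-56 window, Days 345–484) | Week 56, where the collected V25 takes precedence under SAP 3.4.2 |

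**3. Time off drug at each week-82 limit.**

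- Day 555: (555 − 393)/7 = 23.1 weeks.
- Day 485: (485 − 393)/7 = 13.1 weeks.

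BMI SDS needs height, and the SAP does not say which table governs it. If Table 3-2 does, windowing alone still admits values from about half-way through follow-up.

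**4. Illustrate the size on the literal reading.** The documents give neither a follow-up withdrawal rate nor a regain curve. Assume that a share f of week-56 attenders has an early V30, with timing uniform over 26 weeks. Let g(t) be the fraction of the 26-week regain reached t weeks after week 56. The arm's mean rebound is then understated by f × (1 − mean of g).

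- Linear regain: g = t/26, with mean 0.50.
- Fast regain (8-week time constant): g = (1 − e^(−t/8))/(1 − e^(−26/8)), with mean 0.733.

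| f | Linear | Fast |
|---|---|---|
| 5% | 2.5% | 1.3% |
| 10% | 5.0% | 2.7% |
| 20% | 10.0% | 5.3% |

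If regain has levelled off before the early visits, the bias is about zero. If weight overshoots and then falls, the sign reverses.

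**The case against.** **The SAP may already move the record.** The general sentence re-aligns all visits, and the tables give V30 its own window. This stands in part: it cannot be said that an early V30 will certainly keep the week-82 label. But the general sentence is conditional on windows being used, while the limiting sentence is specific to this trial. The two need reconciling on either reading.

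**Early V30 records may be few.** Protocol 6.5 counts a subject as withdrawn only when further contact is declined, and 8.1.9 asks the investigator to aim for the procedures. Some leavers will provide no V30 and are already missing. This stands, and it is why the 5–20% is an assumption.

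**Setting early values to missing could make matters worse.** Suppose Table 3-2 governs, imputation starts from week 56 and placebo does not change after week 56. Under linear regain, half the early values become missing and lose all regain (0.5f). The other half keep the label and lose 25% on average (0.125f). The total is 0.625f against 0.50f now, or 3.1–12.5% instead of 2.5–10%. If every early value were set missing, the loss would be f, or 5–20%. This does not defeat the fix. Imputing the week-82 value from placebo week-82 data with the randomisation baseline as covariate puts the subject at placebo level, so the change from that subject's own week 56 includes a return to placebo. The loss arises mainly if week 56 is the imputation baseline. The objection does show that the SAP must name that baseline and add a sensitivity analysis.

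**Conclusion.** The gap holds as an unresolved inconsistency and a missing rule. The protocol produces V30 records at any time after V25, the trial-specific SAP sentence leaves them unwindowed, and other SAP text and both window tables contradict that. It merits correction because week 56–82 rebound is a stated objective. Every affected endpoint is supportive, and the primary week-56 analysis is untouched.

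A reader might infer that the plan understates rebound, and does so in favour of liraglutide. The documents do not support that. The direction within each arm requires regain that continues to week 82, which is not stated. The size, roughly 1–10% of an arm's mean rebound, rests on the assumed 5–20% share, uniform timing and the two regain shapes. The between-arm difference shrinks by the same proportion only if the early-V30 share, timing and regain shape match across arms. Otherwise its bias depends on leaving times and regain in both.

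**What to change.** - Amend the limiting sentence in SAP 3.4.1.1 along these lines: *windowing applies to the V25, V26 and early V30 (Protocol 8.1.9) records of subjects who discontinue or withdraw*. Reconcile it with the later sentence that re-aligns all visits.
- State that for BMI, BMI SDS and body weight the week-82 window is Day 555 onward (Table 3-1), so that the Day 485 limit in Table 3-2 does not apply to them and an earlier V30 is not used as week 82.
- Treat week 82 as missing for those subjects, and state whether the imputation model uses the randomisation or the week-56 value as baseline.
- Add a sensitivity analysis that uses the early V30 value as observed.

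The cost is a few SAP sentences, a little extra programming and slightly more missing week-82 values. No new data are needed.

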8.5.5 Anti-liraglutide antibodies

Blood samples for determination of anti-liraglutide antibodies should be collected from all subjects and sent via central laboratory to special laboratory for analysis; see Section [2](#). Only samples from subjects treated with liraglutide will be analysed for anti-liraglutide antibody development. A randomisation list will be provided to the special laboratory.

Subjects must be instructed to withhold their trial product dose in the morning until blood sampling is performed on the visit.

Samples are analysed by the special laboratory for anti-liraglutide antibody formation including cross reactivity to endogenous GLP-1. Follow up samples that are found to be positive for anti-liraglutide antibodies will be analysed for in vitro neutralising effect to liraglutide. Antibody positive follow up samples that are found to cross react with endogenous GLP-1 will, in addition, be analysed for in vitro neutralising effect against endogenous GLP-1. The last-mentioned analyses will be performed by Novo Nordisk A/S. See Sections [8.5.4](#) and [24.2](#).

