8.6 Other assessments

8.6.1 Plasma concentration of liraglutide

Blood samples for assessment of liraglutide plasma concentration should be collected and sent via central laboratory to special laboratory for analysis; see Section 2. A randomisation list will be provided to the special laboratory. Samples from randomised subjects will be analysed for liraglutide plasma concentration.

Subjects must be instructed to withhold their trial product dose in the morning until blood sampling is performed on the visit. Any dose taken by mistake in the morning before the visit must be recorded in the eCRF Section made for the purpose.

The subjects must be instructed to complete the dosing diary for liraglutide plasma concentration assessment (see Section 8.6.3.1). The doses, dates and exact time for blood sampling must be recorded in the eCRF.

The blood samples taken at V26, V28 and V30 for liraglutide plasma concentration assessments are not part of the liraglutide pharmacokinetic and pharmacodynamic modelling plan (see Section 17). The purpose of these assessment are to preclude any false negative antibody results. Hence recordings in the subjects' dosing diary and eCRF are not requested for these samples.

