- Documented symptomatic hypoglycaemia: An episode during which typical symptoms of hypoglycaemia are accompanied by a measured plasma glucose concentration ≤ 3.9 mmol/L (70 mg/dL).
- Pseudo-hypoglycaemia: An episode during which the person with diabetes reports any of the typical symptoms of hypoglycaemia with a measured plasma glucose concentration > 3.9 mmol/L (70 mg/dL) but approaching that level.
- Probable symptomatic hypoglycaemia: An episode during which symptoms of hypoglycaemia are not accompanied by a plasma glucose determination but that was presumably caused by a plasma glucose concentration ≤ 3.9 mmol/L (70 mg/dL).

Note: Glucose measurements are performed with capillary blood calibrated to plasma equivalent glucose values

PG: plasma glucose SMPG: Self-measured plasma glucose

Figure 17–2 ADA/ISPAD classification of hypoglycaemia in paediatrics

Anti-liraglutide antibodies

Anti-liraglutide antibodies will be summarised in terms of the number and percentage of subjects per visit that are antibody-positive, antibody-negative, cross-reacting and in vitro neutralising.

In addition, a comparison of the change in HbA_{1c} and body weight between antibody-positive and antibody-negative subjects will be performed using descriptive statistics and graphs. Listings with the individual antibody results will also contain information about the HbA_{1c} levels and body weight measurements. The impact of anti-liraglutide antibodies on safety will be similarly assessed by descriptive comparisons between antibody-positive and antibody-negative subjects.

Bone age assessment

Bone age assessment at baseline and change in bone age assessment will be summarised using descriptive statistics.

ECCG

Summary statistics and the frequencies of shifts from baseline at 30 and 56 weeks will be tabulated for each treatment group.

Pulse

Summary statistics and the frequencies of shifts from baseline to 30 and 56 weeks and from 56 weeks to 82 weeks will be tabulated for each treatment group. In addition, statistical analyses similar to those made for blood pressure will be performed for change from baseline to 30 and 56 weeks.

Laboratory parameters

Summary statistics will be tabulated for each laboratory parameter. The distributions will also be presented graphically using box plots by treatment and week.

For each laboratory parameter, the values will be compared to the relevant reference ranges. The results will be presented as follows:

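### The SAP re-labels discontinuers' V26 antibody samples by study day, so the off-drug follow-up row of the antibody table describes almost only treatment completers

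*SAP*

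**What the plan says.** **Windowing.** SAP 3.4.1 notes that the V25 and V26 records of discontinued and withdrawn subjects do not fall in the endpoint weeks, and continues: "Hence these records will be reallocated to the respective weeks based on analysis day on when the assessments are done by visit windowing concept". Section 3.4.1.1 limits the procedure to those records: "In 4180 the visit windowing will be done only for V25 and V26 visits for prematurely discontinued/withdrawn subjects". Its scope is broad in other respects. "Generally, visit-windows will be used for the data that is summarized by visit", and in Table 3-1 "the days are counted since the date of randomization for both safety and efficacy assessments". Section 3.4.1.2 combines windows for parameters not collected at every visit. Section 3.4.1.3 sends weight, height and related parameters of discontinuers to the x visits and all other parameters to the normal visits. If a reallocated record lands on a visit that already has one, SAP 3.4.2 says "then the collected visit record is used for analysis instead of record which is reallocated to that visit".

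**Antibodies.** Under protocol 8.1.10 a subject who stops trial product has V25 procedures as soon as possible and V26 two weeks after that. Protocol 8.1.2 names V26 among the visits with antibody sampling. Protocol 8.5.5 plans a further assay: "Follow up samples that are found to be positive for anti-liraglutide antibodies will be analysed for in vitro neutralising effect to liraglutide". Protocol 17.4.1.2 sets the reporting: "Anti-liraglutide antibodies will be summarised in terms of the number and percentage of subjects per visit", with antibody-negative, cross-reacting and neutralising results tabulated alongside positive ones.

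Neither document exempts antibody samples from windowing or defines a follow-up category by time off drug.

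**The concern.** For someone who stops early, V26 means off drug for at least about two weeks, whatever the study day. Labelling that sample by days since randomisation replaces this meaning with a calendar week in which most of the other subjects are still on drug.

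Occurrence of anti-liraglutide antibodies is a listed safety endpoint, and the per-visit table is its only planned incidence summary. Followed as written, the rule leaves a follow-up row made up almost entirely of subjects who completed treatment. Off-drug samples of early stoppers are counted with on-drug samples at an earlier visit, or do not enter the table. A neutralising result from such a sample could appear under week 30 or week 56.

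**Working it through.** **Inputs.** Scheduled days from SAP Tables 3-1 and 3-2: V9 = 1, V19 = 211, V25 = 393, V26 = 407, V27 = 449, V28 = 491. SAP 3.4.1.1 ends a window at the midpoint to the next scheduled day, and the next window starts one day later.

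**1. Reproduce the printed windows.** (393 + 407)/2 = 400 and (407 + 449)/2 = 428, so V26 runs from day 401 to 428, as in Table 3-1. All Table 3-1 windows from V10 to V30 reproduce. So do the Table 3-2 height limits from V9 on: (1 + 85)/2 = 43, (85 + 211)/2 = 148, (211 + 295)/2 = 253, (295 + 393)/2 = 344, (393 + 575)/2 = 484.

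**2. Build the antibody windows.** The SAP does not print these. Assumed visits are V9, V19, V25, V26 and later. (1 + 211)/2 = 106, (211 + 393)/2 = 302, (393 + 407)/2 = 400. Hence V9 to day 106, V19 107–302, V25 303–400, V26 from 401. With a V8 baseline (day −14) the first limit is 98.

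**3. Who keeps the V26 label.** The condition is stop day + lag ≥ 401 with stop day ≤ 392. All 392 stop days are weighted equally (assumption).

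| Days from stopping to V26 | Stop days that keep the label | Share of 392 |
|---|---|---|
| 14 | 387–392 (6) | 1.5% |
| 17 | 384–392 (9) | 2.3% |
| 19 | 382–392 (11) | 2.8% |
| 28 | 373–392 (20) | 5.1% |

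These shares are the same with Table 3-1 windows or a V8 baseline, because V26 starts at day 401 in each case.

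**4. Where the others go** (antibody windows of step 2, early V25 on the stop day, lag 14).

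| Stop day | V26 maps to | Outcome | Days |
|---|---|---|---|
| 1–92 | V9, already collected | not used | 92 |
| 93–106 | V19, empty | moved | 14 |
| 107–210 | V19, shared with own early V25 | moved, no tie rule | 104 |
| 211–288 | V19, already collected | not used | 78 |
| 289–302 | V25, empty | moved | 14 |
| 303–386 | V25, shared with own early V25 | moved, no tie rule | 84 |
| 387–392 | V26 | kept | 6 |

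Not used: (92 + 78)/392 = 43.4%. Moved: (14 + 104 + 14 + 84)/392 = 55.1%, of which (104 + 84)/392 = 48.0% of all stop days have two reallocated records in one otherwise empty window.

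With the early V25 at 3 days and V26 at 17 days, 41.8% are not used and 55.9% are moved, or 39.8% and 57.9% with a V8 baseline. If stopping is earlier (exponential, mean 140 days, assumption), 57–60% are not used, 40–43% are moved and 0.4% keep the label.

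**5. Scale.** 228/2 = 114 liraglutide subjects. Protocol 17.1 assumes 40% withdrawal at week 56. If all of it is read as stopping drug with V26 attended, 0.40 × 114 = 45.6 subjects, of whom 45.6 × 6/392 = 0.7 (lag 14) to 45.6 × 20/392 = 2.3 (lag 28) stay in the V26 row.

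**The case against.** Several points on the other side stand and limit the claim.

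- **The split is conditional.** The SAP prints combined windows only for height, and the antibody row of the flowchart cannot be read fully in the text available. Sampling at V28, V30 and the x visits is uncertain. Only the loss of the V26 label is independent of this.
- **Results are not deleted.** A reader might infer that antibody findings are lost or that early stoppers vanish. SAP 3.4.2 decides only which record is used for analysis. Protocol 17.4.1.2 keeps individual results in listings, the neutralising assay is still run, and a week-82 sample, if taken, would still be tabulated. Where two reallocated records share a window, the SAP is silent, so loss is not shown.
- **V26 is not timed from the last dose.** It follows the early V25 by two weeks, and that V25 may itself be delayed.
- **The statement on false negatives concerns another sample.** "The purpose of these assessment are to preclude any false negative antibody results" describes the liraglutide concentration samples at V26, V28 and V30. That antibodies are drawn at V26 because circulating drug could mask them is a fair inference, but the documents do not say so.
- **The counts in step 5 are an upper bound.** Planned withdrawal is not the same as stopping drug and attending V26, and after consent withdrawal sites need only aim for that visit (protocol 8.1.9).
- **The comparisons by antibody status need not be affected.** Nothing says that they use windowed records.

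The table is descriptive, with no formal test. None of this supplies an exemption for antibody samples, and a listing is not an incidence summary.

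**Conclusion.** The concern holds for the visit label. Under SAP 3.4.1.1 as written, about 1.5% to 5% of possible stop days leave a discontinuer's V26 antibody sample in the follow-up row, for lags of 14 to 28 days and uniform stop times. Earlier stopping lowers the share. Only clustering of stops just before week 56 would raise it. The row therefore cannot be read as describing everyone sampled off drug.

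Of the rest, about 40–43% are not used in the by-visit table and 55–58% move to week 30 or week 56 under uniform stopping. These two figures also depend on the antibody schedule and are illustrative. A separate gap is certain: SAP 3.4.1.1 promises a method for multiple assessments in one window, but 3.4.2 has no rule for two reallocated records of one subject.

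The documents do not support reading this as data loss, as a proven bias in the comparisons by antibody status, or as a threat to the primary analysis.

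**What to change.** In SAP 3.4.1.1, exempt anti-liraglutide antibody and liraglutide concentration samples from windowing, and only those. A blanket exemption of V26 could change the weight and BMI records used in the efficacy analyses, so those parameters should stay as they are.

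Then:

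- Report discontinuers' V26 antibody samples under the nominal off-drug follow-up visit. The label should not promise an exact interval since the last dose.
- Show their early V25 samples in a separate row, at premature discontinuation. With the half-life of about 13 hours given in protocol 5.5, a sample taken 3 days (72 hours) after the last dose would have 0.5^(72/13) ≈ 2% of the drug left, so pooling it with on-drug week-56 samples would repeat the mixing.
- Add the number and percentage of liraglutide subjects who are antibody-positive, cross-reacting or neutralising at any post-baseline sample. No visit label can alter that count.
- For parameters that remain windowed, state in 3.4.2 which record is used when two reallocated records share a window.

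The cost is a few lines of SAP text and minor programming, with no new data. The follow-up row will mix calendar weeks, which suits a visit timed from stopping.
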